5.3.6 Other Considerations

Not Applicable.

5.4 EFFICACY ANALYSES

5.4.1 Primary Efficacy Analysis

Regarding the primary endpoint, the null hypothesis is that there is no difference in the mean change from baseline in CDR-SB at 24 months between elenbecestat 50 mg per day and placebo; the corresponding alternative hypothesis is that there is a difference in the mean change from baseline in CDR-SB at 24 months between elenbecestat 50 mg per day and placebo.

The primary analysis will be based on the ITT philosophy without regard to adherence to treatment. All observed data will be included in the primary analysis, regardless of treatment discontinuation or change in concomitant AD medications. The primary analysis of the change from baseline in CDR-SB at 24 months will be performed to compare elenbecestat 50 mg per day versus placebo using a MMRM on the FAS. The MMRM model will include baseline CDR-SB and baseline CDR-SB by visit interaction as a covariate, with treatment group, visit, randomization stratification variables (ie, region [7 levels], clinical disease staging [MCI due to AD, early stage of mild AD], and concurrent AD medication use at randomization (Visit 2) [yes, no]), *ApoE4* status, and treatment group-by-visit interaction as fixed effects. An unstructured covariance matrix will be employed to model the covariance of within subject effect and the Kenward-Roger approximation will be used to estimate the denominator degrees of freedom; if MMRM fails to converge then a covariance structure with fewer parameters from the following list will be employed according to the prespecified order in the list until the MMRM converges. The list of covariance structure will include Heterogeneous Toeplitz, Toeplitz, Heterogeneous Compound Symmetry, and Compound Symmetry. If a structured covariance is used, then the sandwich estimator will be used to estimate variance of the treatment effect estimator.

This primary analysis will include all observed post baseline data of the change from baseline in CDR-SB without imputation of missing values. The least squares (LS) means and difference in

LS means between elenbecostat treatment group and placebo, and corresponding 95% confidence interval (CI) will be presented.

Sensitivity/Supplementary Analyses

- 1). An MMRM analysis will be performed on the PPS.
- 2). To minimize the impact of intercurrent events (i.e., treatment discontinuation or change in concomitant AD medications), an MMRM analysis will be conducted on both FAS and PPS, by censoring the data after intercurrent events (i.e., treatment discontinuation, initiation of new AD medications [AChEI or memantine] and/or change in dose of current AD medications).
- 3). An ANCOVA model will be used after multiple imputation (MI) to evaluate the impact of missing data in both FAS and PPS. The following steps are described for multiple imputation.

Step 1 (imputing missing data): The dataset will be converted into monotone missing pattern by imputing intermediate missing data using MCMC approach first. The monotone data will then be imputed with monotone regression method. The imputation regression model will include treatment group, baseline CDR-SB and all available change from baseline in CDR-SB at post-baseline visits. There will be 1000 imputations, ie, 1000 imputed completed datasets, created with a predefined seed number (seed=2609). SAS PROC MI will be used to implement the imputation procedure. The sample SAS statement can be found in [Section 9](#).

Step 2 (performing ANCOVA using each imputed dataset): The ANCOVA model with factors of treatment group, randomization stratification variables (ie, region [7 levels], clinical disease staging [MCI due to AD, early stage of mild AD], and concurrent AD medication use at randomization (Visit 2) [yes, no]), *ApoE4* status, and baseline CDR-SB as a covariate will be applied to each imputed dataset. SAS PROC MIXED will be used for the ANCOVA. The sample SAS statement can be found in [Section 9](#).

Step 3 (combine results): Resulting treatment effect parameter estimators and standard errors from each of 1000 multiple imputed datasets from Step 2 will be combined using SAS PROC MIANALYZE to obtain the pooled treatment effect and variance parameter estimators according to Rubin's rules ([Rubin, 1987](#)). The sample SAS statement can be found in [Section 9](#).

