3.2 OVERALL STUDY DESIGN AND PLAN

This study is a 24 month treatment, multicenter, double-blind, placebo-controlled, parallel group Core Study with an open-label Extension Phase in EAD including mild cognitive impairment (MCI) due to AD and the early stages of mild AD. In addition, the MCI due to AD population will also be consistent with the research criterion for “Prodromal AD” in that episodic memory will be impaired on a list-learning task (International Shopping List Task [ISLT]). The Extension Phase is available for subjects who complete the Core Study, including the 3-month follow-up, and provides subjects with open-label treatment with elenbecestat for 24 months, or until commercial availability of elenbecestat or a lack of positive benefit-risk is determined, whichever comes first.

Study E2609-G000-301 and Study E2609-G000-302 will be combined, with a total of approximately 1900 randomized subjects; at least 850 subjects will be randomized in each study.

In this Core Study, subjects will be randomized, in a double blind manner, to receive either placebo or elenbecestat 50 mg per day (in 1:1 randomization ratio) for 24 months. Randomization will be stratified according to region (7 levels), clinical disease staging with no more than approximately 25% of the randomized subjects diagnosed with the early stages of mild dementia due to AD, and concurrent AD medication use. The 7 levels of the region are:

1. North America
2. Western Europe (including Oceania region and South Africa)
3. Eastern Europe
4. Japan
5. China
6. Other Asian countries
7. South America

The study is designed to have more frequent visits focused on safety assessments during the first 3 months of treatment.

Three longitudinal biomarker substudies will evaluate the effects of study treatment on the underlying pathophysiology of AD using amyloid PET, tau PET and/or CSF biomarkers. Participation in the substudies is optional and will require specific consent that will not affect

enrollment or treatment in the main study. The tau PET substudy will be offered to study-eligible subjects from select geographical sites (based on proximity to the tau PET ligand manufacturing sites) in the US who have an amyloid positive study-specific PET scan and who have also consented to participate in the amyloid PET substudy. Tau PET scanning will be performed using a sponsor-supplied tau PET imaging agent, eg, PI-2620.

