5 STATISTICAL METHODS

Statistical analyses will be performed by the sponsor or designee after the Core Study is completed and the database is locked and released for unblinding. All statistical analyses will be performed based on the pooled data from 2 studies (E2609-G000-301 and E2609-G000-302). The analyses will also be performed within each study for study disposition, demographic and baseline characteristics, primary endpoint, secondary endpoints, extent of exposure and key adverse event tables. The details are specified in Table, Listing and Graph (TLG) shell. Statistical analyses will be performed using Statistical Analysis System (SAS) software or other validated statistical software as required. All statistical tests will be based on the 5% (2-sided) level of significance.

All descriptive statistics for continuous variables will be reported using mean, standard deviation (SD), median, minimum and maximum. Categorical variables will be summarized as number (percentage) of subjects.

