5.3 DATA ANALYSIS GENERAL CONSIDERATIONS

5.3.1 Pooling of Centers

This study has used region as a stratification factor for randomization, therefore, there is no plan to pool any other type of centers or sites.

The regions and corresponding countries that might be included and are grouped together in a particular region are:

1. North America: US, and Canada
2. Western Europe (including Oceania region and South Africa): Australia, Austria, Denmark, Finland, France, Germany, Italy, Portugal, South Africa, Spain, and United Kingdom
3. Eastern Europe: Bulgaria, Croatia, Czech Republic, Greece, Hungary, Poland, Russian Federation, and Slovakia
4. Japan
5. China
6. Other Asian countries/regions: Singapore, South Korea, and Taiwan
7. South America: Argentina, Chile, and Mexico

Czech Republic is incorrectly listed in IxRS as part of Western Europe and Australia is incorrectly listed in IxRS as part of Other Asian countries (both for E2609-G000-301). The correct list shown above will be used for the any analyses except the adjustments for covariates of interest to follow intent to treat (ITT) principle.

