5.3.2 Adjustments for Covariates of Interest

The primary, secondary, and exploratory efficacy endpoints will include the stratification variables (region, concurrent AD medication use, clinical disease staging), *ApoE4* status, and baseline value of the endpoint (if applicable) as covariates. For mixed-effects models for repeated measures (MMRM), the baseline-by-visit interaction will also be included. To follow ITT principle, the classification used at randomization will be used for the adjustments for covariates of interest.

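### The pooled efficacy models have no term for study, although subjects were randomised within 301 and 302; the cost is a little precision, not validity

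*SAP*

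**What the plan says.** Section 5 sets the analysis basis: "All statistical analyses will be performed based on the pooled data from 2 studies". Section 3.2 gives a combined total of about 1900, requires that "at least 850 subjects will be randomized in each study", and describes allocation "in 1:1 randomization ratio". On strata it says: "Randomization will be stratified according to region (7 levels), clinical disease staging with no more than approximately 25% of the randomized subjects"; concurrent AD medication use is the third factor.

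For the primary MMRM, section 5.4.1 says: "The MMRM model will include baseline CDR-SB and baseline CDR-SB by visit interaction as a covariate, with treatment group, visit, randomization stratification variables". The remaining terms are ApoE4 status and treatment-by-visit. The general covariate rule in 5.3.2 lists the stratification variables, ApoE4 and baseline, with baseline-by-visit for MMRMs. Study is also absent from:
- the ANCOVA after multiple imputation (5.4.1 and the code in section 9);
- the key and other secondary MMRMs and the Cox models (5.4.2);
- the ANCOVA for tau PET and CSF biomarkers (5.4.3).

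Study appears only through separate analyses. Section 5 asks for within-study analyses of the primary and secondary endpoints, and 5.3.4 repeats this for efficacy. Section 7 then withdraws the study-level analysis of amyloid PET SUVR.

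**The concern.** An analysis normally carries the factors that structured its randomisation. Section 5.3.2 does this for region, staging and AD medication, using the classification at randomisation on ITT grounds. Study looks like the layer above those three.

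The SAP does not say outright that the two studies had separate randomisation lists. That is inferred from two places: section 3.2 counts subjects as randomised in each study, and section 5.3.1 describes an IxRS coding problem that applies to 301 only ("Czech Republic is incorrectly listed in IxRS as part of Western Europe and Australia is incorrectly listed in IxRS").

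If the studies differ in mean CDR-SB change after covariate adjustment, a model without study puts that difference into residual variance. The estimated standard error is then slightly too large, and the pooled result invites a question that one more term would have answered.

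**Working it through.** **The plan's own figure.** Inputs from section 4: placebo change 1.46, reduction 25%, SD 2.05, two-sided alpha 0.05, power 90%, dropout 30%.
- Difference: 0.25 × 1.46 = 0.365.
- n per arm = 2(1.960 + 1.282)² × 2.05² / 0.365² = 663.
- With dropout: 663 / 0.70, rounded up, = 948 per arm, or 1896 in total. The SAP states 1900, so its figure reproduces.
- Power with 665 completers per arm (950 × 0.70): 90.1%.

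**Loss of precision.** Let d be the residual between-study difference in SD units and p the share of subjects from 301. Omitting study multiplies the standard error by √(1 + p(1−p)d²). Appendix 9.1 of the DSMB charter gives N = 1169 for 301. Taking 850 for 302 (an assumption, the minimum in section 3.2), p = 1169/2019 = 0.58 and p(1−p) = 0.2436. The documents give no value for d, so a range is shown.

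| d (assumed) | SE inflation |
|---|---|
| 0.1 | √1.00244 − 1 = 0.12% |
| 0.2 | √1.00974 − 1 = 0.49% |
| 0.3 | √1.02192 − 1 = 1.09% |

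These ratios depend on the split and on d, not on the number of subjects.

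**Effect on design power.** Let D be the difference in CDR-SB points, with a 50:50 split. The SD without the study term is √(2.05² + D²/4). With the term, power is 90.1%.

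| D (assumed) | SD without study | Power without study |
|---|---|---|
| 0.2 | 2.052 | 90.0% |
| 0.3 | 2.055 | 89.9% |
| 0.5 | 2.065 | 89.7% |
| 1.0 | 2.110 | 88.4% |

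**Type I error and bias.** A simulation used 1330 observed subjects, 1:1 allocation within each study, and 5000 runs for each of D = 0, 0.3, 0.5 and 1.0. The Monte Carlo standard error near 5% is √(0.05 × 0.95/5000) = 0.3 points.
- Rejection under the null: 0.043 to 0.050 without the study term, 0.045 to 0.052 with it.
- Mean estimated difference under the alternative: −0.363 to −0.367 without the term, −0.364 to −0.369 with it, against a true −0.365.

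There is no inflation and no visible bias. At D = 1.0 the model without study rejects slightly less often than 5%, as expected when the standard error is overstated.

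**The case against.** The strongest reply is that this is a precision choice with almost no consequence. That largely stands. Even the 1.1% figure needs a 0.3 SD gap: 0.3 × 2.05 = 0.62 points, which is 42% of the assumed placebo decline (0.62/1.46) and 1.7 times the target effect (0.62/0.365). The gap must also remain after adjustment for baseline, staging, region, AD medication and ApoE4, under a common design. Study is not singled out everywhere, either. The slope model has no stratification factor at all, and the imputation regression uses only treatment, baseline and visit values.

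Four stronger readings are tempting, and the documents do not support them.

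- *The 301 region coding makes a study term necessary.* A study main effect would not repair a region level that mixed different countries. Sections 5.3.1 and 5.3.2 keep the as-randomised codes deliberately. The country list covers countries that might be included, and nothing says whether 302 enrolled in the Czech Republic or Australia.
- *A later start of 302 distorts the late visits.* The first DSMB forms (April 2017 for 301, August 2017 for 302) only suggest a later start. Visits are counted from first dose (section 8.2). A shift in study mix over visits would affect both arms, and so the visit means, not the randomised contrast.
- *The estimate is biased.* That would require the arms to differ in study share among those observed at 24 months. The shift is D times that imbalance: 0.5 × 0.02 = 0.010, or 1.0 × 0.05 = 0.05, which is 14% of 0.365. Both inputs are assumed; the documents show no such imbalance.
- *Consistency between studies goes unexamined.* The within-study analyses in sections 5 and 5.3.4 largely cover it. The exception is amyloid PET, third in the testing order of 5.3.3, whose study-level analysis section 7 removes.

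**Conclusion.** The point holds as a modest improvement in precision and in agreement with the randomisation structure. No pooled efficacy model in SAP v2.0 names study. Under 1:1 allocation within each study, this does not bias the treatment effect or raise type I error. It costs about 0.1% to 1.1% in standard error for an assumed residual difference of 0.1 to 0.3 SD, and 0.1 to 1.7 points of design power for assumed differences of 0.2 to 1.0 CDR-SB points.

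The conclusion assumes that randomisation was separate by study, which is inferred rather than stated. The sizes rest on assumed between-study differences and study splits, and the power figures describe the planned sample, not the smaller one left by early termination.

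**What to change.** Add study (301/302) as a fixed effect to the pooled MMRM and ANCOVA models, in 5.3.2, 5.4.1, 5.4.2, 5.4.3 and the ANCOVA code in section 9. Add study-by-visit to the MMRMs if the model supports it; sparse 24-month data after early termination may prevent that. Stratify the Cox models by study.

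Report the treatment-by-study contrast descriptively, beside the within-study analyses already planned. Do the same for amyloid PET if data allow.

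The cost is SAP wording and one classification variable. For the primary MMRM this uses 1 degree of freedom for study and 7 for study-by-visit, given the eight post-baseline visits in Table 4. No new data are needed and the sample size does not change.

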5.3.5 Handling of Missing Data

Efficacy endpoints

The primary endpoint will be analyzed using MMRM assuming missing at random (MAR). The same method will be used for key secondary endpoints, other secondary endpoints, exploratory endpoints and biomarker endpoints if appropriate.

In addition, all missing values will be imputed using multiple imputation assuming MAR with analysis of covariance (ANCOVA) as sensitivity analysis for primary analysis. The detailed programs are shown in [Section 9](#).

Clinical Assessment

If any item is missing within the CDR, ADCOMS, ADAS-cog₁₁, ADAS-cog₁₄, MMSE, FAQ, and ADAS-cog₁₄ Word List (immediate recall and delayed recall) then their respective total scores will be missing.

Laboratory values

If the values include non-numerical symbols “>”, “<”, “<=” and “>=”, they will be imputed using the following rule.

- For < values impute with value - 1
- For > values impute with value + 1
- For >= values or <= values impute with value

If the least significant digit of the value is after the decimal point, increase/decrease by the smallest unit of that digit (ex. for, “>7.3”, use 7.4 which is calculated by $7.3 + 0.1$).

Plasma/CSF PD/Biomarkers

Values >upper limit of quantification (ULOQ) or < lower limit of quantification (LLOQ) will be imputed using ULOQ or LLOQ respectively.

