9 PROGRAMMING SPECIFICATIONS

The rules for programming derivations and dataset specifications are provided in separate documents.

The following sample SAS statement provides the framework for the MI method:

CONVERT DATASET INTO MONOTONE MISSING DATA PATTERN (IMPUTING ARBITRARY MISSING DATA):

```
PROC MI data=<dataset> nimpute=1000 seed=2609 out=<dataset1>;
```

```
VAR base visit1 ... visit8;  
MCMC chain=multiple impute=monotone;  
EM maxiter=15000;  
BY trt01pn;  
RUN;
```

IMPUTE MISSING VALUES:

```
PROC MI data=<dataset1> nimpute=1 seed=2609 out=<dataset2>;  
CLASS trt01pn;  
MONOTONE regression (/details);  
VAR trt01pn base visit 1 ... visit8;  
BY _imputation_;  
RUN;
```

PERFORMING ANCOVA:

```
PROC MIXED data=<dataset2>;  
CLASS trt01pn clindem curadmed apoe4st region;  
MODEL chg = base trt01pn clindem curadmed apoe4st region;  
LSMEANS trt01pn / DIFF CL;  
BY _imputation_;  
ODS output diffs=<dataset3>;  
RUN;
```

COMBINE RESULTS:

```
PROC MIANALYZE data=<dataset3>;  
MODELEFFECTS estimate;  
STDERR stderr;  
RUN;
```

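### Every analysis of the primary endpoint assumes data missing at random, including the one meant to show the impact of missing data, so none tests a departure from that assumption

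*SAP*

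**What the plan says.** Section 5.3.5 of SAP v2.0 says of the primary analysis "The primary endpoint will be analyzed using MMRM assuming missing at random (MAR" and, of the supplementary one, "all missing values will be imputed using multiple imputation assuming MAR with analysis of covariance (ANCOVA) as sensitivity analysis for primary analysis".

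Section 5.4.1 then lists three sensitivity or supplementary analyses:

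- **Item 1** repeats the MMRM on the per-protocol set.
- **Item 2** repeats it on both the FAS and the PPS after removing data that follow treatment discontinuation or a change in AD medication.
- **Item 3** is the only one given a missing-data purpose: "An ANCOVA model will be used after multiple imputation (MI) to evaluate the impact of missing data in both FAS and PPS".

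For item 3, Step 1 states: "The imputation regression model will include treatment group, baseline CDR-SB and all available change from baseline in CDR-SB at post-baseline visits". The sample code in section 9 agrees. The MCMC step has "VAR base visit1 ... visit8", run by treatment arm, and the monotone step has "VAR trt01pn base visit 1 ... visit8". The ANCOVA that follows has more terms: "MODEL chg = base trt01pn clindem curadmed apoe4st region".

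SAP v2.0 contains no delta-adjusted, tipping-point, reference-based or other missing-not-at-random analysis of the primary endpoint.

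**The concern.** A sensitivity analysis for missing data should change the assumption that cannot be checked from the observed data. Here that assumption is MAR: given what was observed, subjects with no 24-month value would have behaved like similar subjects who have one. Item 3 keeps the assumption and changes only the computing route, so it will tend to agree with the MMRM whether or not MAR is true.

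The plan allowed for 30% dropout (section 4). The DSMB recommendation form of 11 September 2019, which predates SAP v2.0, reports an adverse event profile worse than placebo and a more consistent negative trend at 24 months. Dropout related to outcome, and differing between arms, was therefore foreseeable. Section 7 records that the sensitivity analyses were revised after termination, but no departure from MAR was added. The 24-month CDR-SB test still heads the testing hierarchy in section 5.3.3.

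**Working it through.** **1. Assumption made by each analysis**

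| Analysis | Data used | Assumption for missing values |
|---|---|---|
| Primary MMRM | FAS, all observed | MAR (stated in 5.3.5) |
| Item 1, MMRM | PPS | MAR (same likelihood model) |
| Item 2, MMRM | FAS and PPS, data after intercurrent events removed | MAR, with more values missing |
| Item 3, MI then ANCOVA | FAS and PPS | MAR (stated in 5.3.5) |

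**2. The plan's sample size (section 4)**

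Inputs: placebo mean change 1.46, SD 2.05, 25% reduction, 90% power, two-sided 0.05, 30% dropout, 1:1 allocation.

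- Effect: 0.25 × 1.46 = 0.365.
- n per arm = 2 × (1.960 + 1.282)² × 2.05² / 0.365² = 663.
- With dropout: 663 / 0.70 = 948 per arm, 1896 in total. The exact t-test gives 664, then 949 per arm, 1898 in total.

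The stated 1900 is reproduced. The figures serve here only to set a scale.

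**3. Scale of a departure from MAR**

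- Completers per arm: 950 × 0.70 = 665.
- SE = 2.05 × √(2/665) = 0.1124. Power under MAR is 90.1%.
- If a fraction f of elenbecestat subjects is missing and each is d points worse than MAR predicts, the benefit shrinks by f × d. It loses significance when 0.365 − f × d = 1.96 × SE.
- At f = 0.30: d = (0.365 − 0.2204) / 0.30 = **0.48 points**.
- If missing elenbecestat subjects have no benefit over placebo, the effect is 0.70 × 0.365 = 0.256. Power is then Φ(0.2555/0.1124 − 1.96) = Φ(0.31), about **62%**.

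SAP v2.0 does not give the actual fraction missing, so a range is assumed:

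| Missing | Power under MAR | Power, no benefit if missing | Tipping d |
|---|---|---|---|
| 20% | 94% | 79% | 0.79 |
| 30% | 90% | 62% | 0.48 |
| 40% | 85% | 44% | 0.32 |
| 50% | 78% | 28% | 0.21 |
| 60% | 69% | 16% | 0.12 |

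**4. Whether agreement gives any warning**

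This is an illustrative simulation with assumed covariate effects and dropout model: 2,000,000 subjects, one intermediate visit, 32% missing at 24 months. The chance of being missing on elenbecestat rises with worsening after the intermediate visit. The full-data difference was −0.366. MAR imputation gave −0.807 without the omitted covariates and −0.803 with them. The two agree closely, yet both overstate benefit by about 0.44 points.

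**5. The omitted covariates**

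Treatment, baseline CDR-SB and the CDR-SB changes at the visits are in the imputation model. Region, staging, AD medication and ApoE4 are not.

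- When dropout depended on the earlier visit only, imputation with and without the covariates gave the same answer, −0.365.
- When dropout also depended on ApoE4 in opposite directions by arm, the results were −0.365 with and −0.354 without, a cost of about 0.01 points.
- A harsher assumed case had 25% mild dementia declining 1.2 points faster, dropout log-odds for staging of 1.2 on active and 0.3 on placebo, and about 30% missing. Bias was −0.054 without staging, −0.056 with staging as a main effect, and about zero only with staging by visit. The SAP's MMRM has staging as a main effect only.

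**The case against.** **Stopping drug is not the same as missing data.** Section 3.2 asks subjects who stop early to return at 12 and 24 months. Section 5.4.1 keeps all observed data whatever the adherence, and section 8.2 assigns early-discontinuation, follow-up and return assessments to analysis visits. Comparing item 2 with the primary analysis also shows how far off-treatment values differ from what MAR would extrapolate. All of this stands and narrows the problem. It says nothing about subjects who leave the study and are not seen again.

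**Item 3 is not wholly redundant.** Its MCMC step is fitted by arm, and the imputation stays unstructured if the MMRM has to fall back to a simpler covariance. It therefore checks some modelling choices, which is why the point is limited to departures from MAR. To say that item 3 shows nothing about missing data would go too far.

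**Much of the missingness is probably administrative.** Values lost to sponsor termination are plausibly MAR, and the fix leaves them there. A reader might go further and infer that most 24-month values are missing, since Appendix 9.1 of the DSMB charter labels a column as 5% of subjects for September 2019. That label gives the review timing in a conditional-power table. It is not a count of the final FAS.

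**The trials were stopped with no evidence of potential efficacy, so a stress test of a positive result matters less.** This limits the practical consequence. But the test remains formally confirmatory, and MAR can mislead in the other direction: if elenbecestat subjects who left did worse than MAR predicts, the planned analyses would understate harm.

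**Conclusion.** The point holds in this form: all four analyses of the primary endpoint share the MAR assumption, and the one assigned to missing data does not depart from it. On planning figures, significance at an observed 0.365 would be lost at a penalty of about 0.48 points with 30% missing, or between 0.79 and 0.12 points across an assumed 20% to 60%. These figures take the SE from completers, the SAP's SD of 2.05, and a penalty on the active arm only. They show scale and do not predict the trial's result.

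The covariate omission is a real mismatch between the imputation and the ANCOVA, but secondary. A reader might infer that the imputation assumes a cruder MAR than the MMRM and is therefore materially biased. The documents do not support that. The MMRM carries these factors as main effects only, and in the scenario least kind to the imputation it was as biased as imputing without staging. Without arm-differential dropout no bias appeared.

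This is a cheap improvement that should be made. It does not invalidate the primary analysis.

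**What to change.** 1. **Keep the present MAR imputation** for intermittent gaps and for subjects whose follow-up was ended by sponsor termination.
2. **Add to item 3 a departure from MAR** for subjects who left the study for any other reason. Either add a fixed penalty to imputed elenbecestat values and raise it in steps until the conclusion changes, or impute from the placebo arm. At 30% missing, each 0.1-point step moves the difference by 0.3 × 0.1 = 0.03. If the primary result is not significant, report the estimate and interval across the same range of penalties.
3. **Classify subjects by the primary reason for study withdrawal.** Section 5.2.2 already lists sponsor termination separately from adverse event, inadequate therapeutic effect, loss to follow-up, subject choice and withdrawal of consent. No new data are needed.
4. **Add region, staging, AD medication and ApoE4 to the imputation**, so that it matches the Step 2 ANCOVA. With seven regions and two-level ApoE4 status this means 6 + 1 + 1 + 1 = 9 indicators. In the by-arm MCMC step these may be unstable where late visits are sparse, so a fallback should be stated (for example, the monotone step only). Study is in neither the MMRM nor the ANCOVA and need not be added for this purpose.

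The cost is some extra SAS code, a short paragraph in section 5.4.1 and one table.
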